7.0 Overview of Planned Analysis

7.1 Changes from Protocol

To align with published reports of platelet response, an additional requirement of 'an increase from baseline of $\geq 20 \times 109/L$ ' was added to the definition of a therapeutic platelet count.

7.2 Interim Analysis and Key Results

After the completion of Part A the database was locked and unblinded and an interim reportprovided.

Dose escalation reports during Part A and B will be prepared by a process not covered by this SAP.

7.3 Final Analysis

Draft TFLs (Tables Figures and Listings) will be provided after database lock. After Sponsor comments have been incorporated, the TFLs will be incorporated in the first draft CSR.

8.0 Data Review

8.1 Data Management

Data handling and transfer will take place under the PRA Data Management Plan for the study.

8.2 Acceptance of Data for Summarization

Programming of analysis datasets and TFLs may be ongoing during the data management of the study. However, programming of analysis datasets and TFLs will be completed and quality controlled (QC'd) after database lock. Only quality assured (QA'd) results released by the Safety Laboratory, Bioanalytical Laboratory, or other external data source will be used for the programming of analysis datasets and TFLs for the final report. Any data values requiring investigation or corrections that are identified while programming the analysis datasets and TFLs will be sent to the project Data Manager. If the issue affects the TFLs the Programmer or Statistician who identified the issue will follow it to resolution.

9.0 Definitions and General Analysis Methods

9.1 Analysis Data Presentation

9.1.1 Rounding

In listings, data will be presented with the same precision as the original data. Derived data will be rounded for presentation purposes.

Individual values and descriptive statistics of PK concentrations and PK parameters will generally be presented with 3 significant figures. Values greater than 999 will be presented as integers. The t_{max} will be reported with 2 decimals.

For all other summaries, all descriptive statistics will be presented with the same precision (number of decimals) as the data they are calculated from.

P-values will be reported to four decimal places; p-value less than 0.0001 will be reported as p < 0.0001.

9.1.2 Imputation

Unless otherwise noted, data will not be imputed.

9.1.3 Descriptive Statistics

Unless otherwise indicated, continuous variables will be summarized with the following descriptive statistics: n (number of observations), (arithmetic) mean, standard deviation (SD), minimum (min) value, median, and maximum (max) value. For PK and PD data, nblq (number of observations below the limit of quantification), CV, geometric mean, and coefficient of variation of the geometric mean (geoCV) will be presented additionally. If the total number of subjects per treatment is lower than 3 then the only descriptive statistics presented will be arithmetic mean, minimum and maximum.

Categorical data will be summarized with frequencies and percentages. Percentages by categories will be based on the number of subjects exposed within a treatment.

For categorical data the categories will be presented in the tables exactly as they appear in the eCRF / Database.

9.1.4 Pooling

Summary statistics will be calculated by population (healthy volunteers or ITP), treatment (investigational product [placebo, M254, or IVIG], dose, and dose frequency) and time point (if applicable). Summary statistics in Part B and C will be calculated by cohort and treatment. Summary statistics in Part D will be calculated by total planned number of doses received, by total actual number of doses received and overall. Placebo data will be pooled for Part A. For the AEs presentation data from different dose levels per part will be summarized per dose and also different M254 doses will be pooled and summarized together (M254 overall). Data from the corresponding M254 dose levels in Parts B and C will be pooled together (in addition to presentation by part, cohort and treatment).

9.1.5 Unscheduled Measurements

Unscheduled measurements will be included in the listings. For Part A, unscheduled measurements will be excluded from the descriptive statistics and statistical analysis (with the exception of unscheduled measurements used for baseline).

9.2 Analysis Data Definitions

9.2.1 Baseline Definition

Unless otherwise stated, baseline for post-dose evaluations is defined as the last observation recorded before the first study drug administration. In case of Part B, C and D, baseline will be the last observation recorded before the first study drug administration in each period. The last observation can be an unscheduled / repeated measurement. If a pre-treatment observation is missing in a given period then the screening value may be used.

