- a Procedures should occur in the order presented above from top to bottom if more than 1 procedure occurs at the same nominal time. Urine sampling or anything with a specific footnote may be done out of order.
- Only visits required to be at the study site are screening, infusions, the day after an infusion, and Day 29, all others can be done by visiting nurse if patient prefers this option. Visit windows of ±1 day should be used whenever possible; ±3 day windows should only be used when required due to clinical site closures (eg, for holidays or COVID-19-related limited schedules). When visit windows overlap, they must not be combined into a single actual day.
- c Screening weight will be used to determine eligibility and dosing, and will allow up to 1 month for weight variability.
- d Vital signs includes body temperature, supine (after 5 minutes) blood pressure, pulse rate, and respiratory rate. Vital signs will be assessed every 30 minutes during an infusion. For infusions <35 minutes, vital signs assessments may occur just after starting the infusion and just prior to the end of the infusion. Refer to Footnote s for exception.
- c Concomitant Medications and AEs will be assessed throughout the infusion and the study. Subjects will be queried and observed for AEs daily during the confinement period, then at each subsequent clinic visit. Should there be a bleeding event reported by the patient or observed by the physician during examination, the ITP-BAT must be completed, see ITP-BAT in Appendix 6, as well as an AE form.
- Safety labs will include complete blood count (CBC), serum chemistry, coagulation, and coagulation screening lab (at screening only) (see Table 10-1). All safety labs will be assessed by the central lab, except for platelet counts, which should be done locally at all the visits where they are scheduled. In case of an AE that requires additional sampling and the Investigator needs to review the results to determine patient care additional safety labs can be assessed by the local lab.
- The platelet measurement for eligibility must be taken within 96 hours of start of infusion. Platelet sample may be combined with safety labs if sample is taken at the same time. All scheduled platelet measurements must be sent to the central and local lab. If there is insufficient time to review the central lab results an additional local lab sample may be obtained in order to assess eligibility for infusion.

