The SRC will review all safety data for all patients in Part B up to at least 28 days following M254 administration for the last patient. Initiation to Part C will only proceed on the recommendation of the SRC. Part C consists of 2 randomized, unblinded crossover cohorts, to assess safety and PD of a single dose of M254 compared to a single dose of IVIg in ITP patients. The dose of M254 for each of these 2 cohorts will be determined after analysis of the data from Part A and Part B. Each cohort consists of 10 patients with 2 arms in each cohort consisting of 5 patients in each arm, for an overall total of 20 patients in Part C. Following screening to confirm eligibility to participate, in crossover Cohort 1 or Cohort 2, 5 patients in each cohort will be randomized to M254 by IV administration and 5 patients will be randomized to 1000 mg/kg IVIg. Patients will receive 1 dose of either M254 or IVIg, depending on their assigned arm within the cohort on Day 29 if the patients' platelet count returns to ≤15% above baseline level. Patients whose platelets have not returned to ≤15% above baseline dosing level by Day 28 will have platelet determinations weekly until platelets return to ≤15% above baseline up to 56 days post the first M254 or IVIg administration. Patients who do not meet this criteria will receive the second administration of M254 or IVIg, as long as the platelets have returned to $< 50 \times 10^{9}$ /L. If the platelets have not returned to $\leq 15\%$ above baseline and are $> 50 \times 10^{9}$ /L. 10⁹/L, the patient will complete Follow-Up assessments on or around Day 57 post first infusion and be discharged from Part C; and the patient may be replaced. After patients are crossed over to M254 or IVlg, they are followed for an additional 28 days with safety and platelet assessments or until platelet counts return to ≤15% above their baseline level following similar rules to the first dose in Part C.

Figure 4: Part C Schema

IVIg = Intravenous immunoglobulin; TBD = to be determined.

- ^a Patients will be followed for 28 days or until their platelet counts have returned to ≤15% above baseline levels and then crossed to the second period. Patients will again be dosed and followed for an additional 28 days with safety and platelet assessments.

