17.2.2 Platelet Parameters

Missing values in the calculation of any PD parameters will not be imputed and handled as missing values. The PD parameters for all subjects in the FAS set will be estimated from the platelet count-time profiles and platelet count change from baseline-time profiles (as specified in Table 2: PD Parameters). The calculation will be performed using the actual sampling times. If the actual time is missing, the scheduled time will be substituted in order to calculate the PD parameter.

Baseline is defined as the pre-dose sample of each period.

In calculation of AUC, the linear trapezoidal calculation method will be used. Descriptive statistics will be calculated and presented for all derived PD parameters by study part and treatment. In case of Part D by these data will be presented by planned and actual treatment (if the actual number of doses received differs from planned).

Individual PD parameters will be listed, and descriptive statistics will be summarized in tables.

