16.1.9.2 Statistical Methods and Analysis Output

STATISTICAL METHODS AND ANALYSIS OUTPUT

A 4-Part Phase 1/2 Study to Evaluate the Safety, Tolerability, Pharmacokinetics, and Pharmacodynamics of M254 in Healthy Volunteers and in Patients with Immune Thrombocytopenic Purpura

CONFIDENTIAL

PRA code: MMT102EC-170091 Sponsor code: MOM-M254-001

SPONSOR

Momenta Pharmaceuticals, Inc.

AUTHOR

PPD

Statistical Methods MOM2-M254-001/ MMT102EC-170091 30-Nov-2021

TABLE OF CONTENTS

3
3
3
4

1. General

The safety, tolerability, pharmacokinetic (PK) and pharmacodynamic (PD) evaluation was conducted by the Biostatistics Department of PRA. This document describes deviations from the statistical analysis plan (SAP), additional decisions made during analysis and reporting and output of statistical analysis that were not included in the Tables, Figures or Listings.

Statistical analysis was performed using the computer program SAS® for Windows[™] Version 9.4 (SAS Institute Inc.).

PK parameters were derived using validated Phoenix[™] WinNonlin®, Version 8.1 (Certara USA Inc).

2. Deviations from the SAP

In section 16 of the SAP it was planned that the PK parameters of M254 will be calculated from the concentration profiles versus time. However during analysis predose concentrations were observed (as for the IgG). Therefore, the PK parameters calculation for M254 was also based on the changes from baseline of the plasma concentrations versus time profiles. In the M254 change from baseline calculations values below LLOQ were set to the LLOQ value. As the absolute concentration values for PK were not used in the analysis, the TFLs and CSR present figures with change from baseline data only. Section 9.2.1 plans to impute the missing baselines with screening values. In case baseline in period 2 was missing, baseline from period 1 was used instead of the screening value for the PK and PD data. Also: the SAP does not foresee how to treat negative AUC values in the statistical analysis of the platelet data (section 17.2.2.1 of the SAP). These values were not included in the analysis. The statistical analysis for platelet data was repeated for the subjects with baseline below or equal to 30, but in this model baseline as covariate was not included.

3. Statistical Analyses

Primary Statistical Analysis of Platelet Parameters

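### A missing Period 2 platelet baseline may be filled with a value from before the Period 1 infusion, which shifts that patient's Period 2 change from baseline

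*SAP*

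**What the plan says.** SAP 9.2.1 states that for Parts B, C and D "baseline will be the last observation recorded before the first study drug administration in each period", and that "The last observation can be an unscheduled / repeated measurement". It then gives the fallback: "If a pre-treatment observation is missing in a given period then the screening value may be used". For the platelet parameters, SAP 17.2.2 is narrower: "Baseline is defined as the pre-dose sample of each period".

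The statistical methods appendix (16.1.9.2, section 2, deviations from the SAP) reports a different fallback: "In case baseline in period 2 was missing, baseline from period 1 was used instead of the screening value", for the PK and PD data.

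The second Part C infusion depends on a platelet count. SAP 6.0 allows it "on Day 29 if the patients' platelet count returns to ≤15% above baseline level". After weekly counts up to Day 56 there is a second route: "Patients who do not meet this criteria will receive the second administration of M254 or IVIg, as long as the platelets have returned to" below 50 × 10^9/L. The protocol synopsis also prints below 50, while protocol 4.1.3 prints at or below 50; these passages must be reconciled. The footnotes to protocol Table 1-3, whose schedule is repeated for the second infusion, add: "The platelet measurement for eligibility must be taken within 96 hours of start of infusion".

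**The concern.** Screening (Day -28 to -2) and the Period 1 baseline both come before any study drug. If either stands in for the Period 2 baseline, whatever rise is left from Period 1 is counted as response to the Period 2 drug. Change-from-baseline Rmax, AUC0-14 and AUC0-28 are three of the four parameters in the primary model (SAP 17.2.2.1). The fourth, absolute Rmax, is touched only through the baseline covariate.

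Two further outputs could move. The therapeutic-count definition (SAP 17.1.2) requires an increase of at least 20 × 10^9/L from baseline, and a low substitute can meet part or all of that before the second infusion. The appendix also says that negative AUCs were left out of the model, so the choice of baseline can decide whether a record enters it. The data are few: 21 observations were read, with 19 used for AUC0-14 and 17 for AUC0-28.

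**Working it through.** **Scale, from the appendix output (all subjects).** For AUC0-14 the least squares means are 7.9716 (M254) and 9.3800 (IVIg). Their difference is 7.9716 − 9.3800 = −1.4084, as reported. With SE 0.4696 and 8 df, −1.4084 ± 2.306 × 0.4696 gives −2.491 to −0.326, which agrees with the reported interval. The geometric means for M254 and IVIg are:

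- AUC0-14: exp(7.9716) = 2,897 and exp(9.3800) = 11,849 (10^9/L·h)
- AUC0-28: exp(8.6103) = 5,488 and exp(10.1392) = 25,316 (10^9/L·h)
- maximum change from baseline: exp(3.1437) = 23.2 and exp(4.4418) = 84.9 (10^9/L)

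**Shift.** Let B2 be the actual count before Period 2 and B1 the substituted value. SAP 9.2.3 defines change as post-dose minus baseline, so

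Y(t) − B1 = [Y(t) − B2] + (B2 − B1).

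Maximum change moves by (B2 − B1), AUC0-14 by 14 × 24 = 336 h × (B2 − B1), and AUC0-28 by 28 × 24 = 672 h × (B2 − B1). The area shifts are slightly smaller if the change at time zero is fixed at zero.

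**How large the gap may be at crossover.** The entry range is 15 to below 50 × 10^9/L (protocol 5.2.1).

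- 15% route: 0.15 × 15 = 2.25; 0.15 × 20 = 3; 0.15 × 50 = 7.5 as the ceiling.
- Later route, count below 50: almost 50 − 15 = 35 from a baseline of 15, and almost 50 − 30 = 20 from a baseline of 30.

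**Size for one affected patient whose response equals the reported geometric mean.** The baselines are assumptions. Percentages are the shift divided by the M254 / IVIg geometric mean.

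| B2 − B1 | Max change | AUC0-14 shift | AUC0-28 shift |
|---|---|---|---|
| 3 (baseline 20, 15% limit) | 13% / 4% | 1,008: 35% / 9% | 2,016: 37% / 8% |
| 7.5 (ceiling, 15% route) | 32% / 9% | 2,520: 87% / 21% | 5,040: 92% / 20% |
| 20 (ceiling, later route, baseline 30) | 86% / 24% | 6,720: 232% / 57% | 13,440: 245% / 53% |

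**Direction.** In the IVIg-M254 sequence a positive gap inflates M254; in the M254-IVIg sequence it inflates IVIg. If B2 is below B1, both signs reverse.

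**Is a substitute needed?** The infusion proceeds only if a count meets the criterion, that count must fall within 96 hours, and protocol 10.2 requires local results to be entered in the CRF. A footnote to Table 1-3 says that Period 1 follow-up assessments done on the same date need not be repeated for Period 2 Day 1. A usable count can therefore exist without a Period 2 label, and neither SAP 9.2.1 nor 17.2.2 expressly tells the analyst to look for it before falling back.

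**The case against.** The strongest reply is that SAP 9.2.1 already solves the problem. Its main rule takes the last recorded observation before dosing and admits unscheduled values, so read literally it selects the Day 29, weekly or local qualifying count. The fallback is a general, permissive sentence covering all data types, and if the protocol is followed it should rarely apply to platelets. This largely stands and limits how often the problem can arise. It does not remove it: 17.2.2 uses narrower words, and the appendix reports a fallback for PD data that also reaches back before Period 1.

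A reader might infer from the appendix that Part C platelet baselines were in fact substituted. The sentence is conditional, covers PK and PD together, and names neither a part nor a number. A reader might also take the large shifts under the later route as typical. They need a patient who missed the 15% criterion through Day 56, was dosed under the 50 × 10^9/L route, and had no assigned baseline; the documents give no frequency for that combination.

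It is also fair to say that subtracting B2 does not isolate the Period 2 drug effect. If B2 is raised by a fading Period 1 response, removing all of it from every time point can over-correct, especially for the areas. For the same reason, falling back on any last Period 1 count without a time limit could bias the other way. Finally, Part C is exploratory, with no formal hypothesis testing (SAP 6.1 and 9.4.3).

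**Conclusion.** The point holds as a defect in the fallback rule, both as planned and as reported. A value from before Period 1 should not serve as the Period 2 platelet baseline when the design requires a qualifying count close to the second infusion. For an affected patient the shift is exactly (B2 − B1) in maximum change, and 336 h or 672 h times that in the areas. At the 15% limit with an assumed baseline of 20, this is 1,008 in AUC0-14, about 35% of the M254 geometric mean.

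A reader might go further and conclude that carryover has biased the reported M254/IVIg ratios. The documents do not support that. They give neither the number of substituted platelet baselines nor their sequence, the gap can have either sign, and the net effect may be zero. The figures above are per-patient illustrations under stated assumptions, not estimates of bias.

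**What to change.** In SAP 9.2.1 and 17.2.2, state that the Period 2 platelet baseline is the last count before the Period 2 infusion within the 96-hour eligibility window, including Period 1 Day 29, weekly, unscheduled and local-laboratory counts. Exclude Period 2 platelet data from both the screening fallback and the Period 1 baseline fallback. If no such count is recorded, leave the Period 2 change from baseline missing in the primary analysis, and use the pre-Period 1 substitution only as a sensitivity analysis. Re-derive any substituted records and report their number by sequence, stating zero if there were none.

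The cost is a wording change in two SAP sections and re-derivation of whatever records are affected. The downsides are that some baselines may come from a local laboratory, and that a record with no qualifying count is lost from the primary analysis of a small data set.

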9.2.2 Treatment/Subject Grouping

In tables the data will be presented by study part and treatment, and where applicable by sequence. Parts B and C will also have pooled analysis (see Section 9.5).

Label	Definition
Study Part	Part A – SAD HV, Part B – SAD ITP patients, Part C – cross over ITP patients, Part D – fixed dose ITP patients
Study Drug	M254, IVIg, Placebo
Treatment	Part A:
	Placebo, 3 mg/kg M254, 10 mg/kg M254, 30 mg/kg M254, 60 mg/kg M254, 120 mg/kg M254, and 250 mg/kg M254
	Part B [.]
	60 mg/kg M254, 120 mg/kg M254, 250 mg/kg M254, 500 mg/kg M254, 1000 mg/kg IVIg
	Part C:
	The dose of M254 will be determined after analysis of the data from Part A and Part B $$
	1000mg/kg IVIg
	3 or 4 doses of M254 (planned treatment); possibly more than one dose level of M254 as well

9.2.3 Common Variable Derivations

Variable	Data Type	Definition/Calculation
Change from Baseline	All	Post-dose Observation minus Baseline Observation
Analysis Relative Day (Prior to Dose)	All	Date of Measurement minus Dose Date. In case of Part B and C it will be Date of Measurement minus Dose Date in a given treatment period.
Analysis Relative Day (Post-Dose)	All	Date of Measurement minus Dose Date +1. In case of Part B and C it will be Date of Measurement minus Dose Date in a given treatment period +1.

9.2.4 QC

The analysis datasets and the TFLs will be QC'd according to the general PRA EDS QC plan.

9.2.4.1 Critical Data

The QC plan requires datasets be classified as critical or non-critical. As the primary objective of this study is to assess safety, tolerability and PD the datasets considered critical are subject level, AEs and PD (ADSL,

ADAE, ADPD). As these are related to the primary objectives these datasets will be double programmed per the QC plan.

9.2.5 ADaM Datasets and Metadata

The analysis datasets will be generated in accordance with Clinical Data Interchange Standard Consortium (CDISC) Analysis Data Model (ADaM) Version 2.1. At least the following datasets will be generated:

- Subject-Level Analysis Dataset (ADSL)
- Adverse Events Analysis Dataset (ADAE)
- Laboratory Analysis Dataset (ADLB)
- Vital Signs Analysis Dataset (ADVS)
- ECG Analysis Dataset (ADEG)
- Pharmacokinetic Concentrations Analysis Dataset (ADPC)
- Pharmacokinetic Parameters Analysis Dataset (ADPP)
- Pharmacodynamic Concentrations Analysis Dataset (ADPD)
- Pharmacodynamic Parameters Analysis Dataset (ADPDP)

ADaM compliant datasets will be delivered to the sponsor. A define.xmlfile version 2 with the corresponding metadata will be included. Analysis results metadata are excluded.

9.3 Software

The statistical analysis and reporting will be done using SAS[®] for Windows[™] Version 9.4 or higher (SAS Institute, Inc.).

PK parameter calculations will primarily be done using Phoenix[®] WinNonlin[®] version 8.1 or higher (Pharsight, Inc.). Additional PK computations may be performed in SAS[®].

